## 2.4 Clinical Experience with Flotetuzumab

Details of the clinical experience with flotetuzumab may be found in the current version of the **Investigator's Brochure**.

#### 2.5 Risk and Benefit Assessment

The patients expected to enroll in the CP-MGD006-01 study have primary induction failure or early relapsed AML. The administration of study drugs to patients with AML in the CP-MGD006-01 trial could potentially result in clinical benefit such as prevention of disease progression and longer survival.

In reference to safety concerns for severe acute respiratory syndrome coronavirus 2 (SARS-CoV-2), there is currently no known evidence of increased risk for SARS-CoV-2 infection or its exacerbation during treatment with flotetuzumab. No increased risk to patients is anticipated as a result of receiving SARS-CoV-2 vaccines, which are permitted during the study. MacroGenics' medical team will continue to review and monitor patient data and ensure patient safety at all times.

The Sponsor and the principal investigators will provide updates on the impact of prior or concurrent SARS-CoV-2 and the impact, if any, on patient safety as new information becomes available, and implement strategies to ensure patient safety and the validity of the trial.

# **3 STUDY PURPOSE AND OBJECTIVES**

## **3.1 Primary Objective**

To assess the anti-neoplastic activity of flotetuzumab in patients with PIF/ER AML, as determined by the proportion of patients who achieve CR/CRh.

## **3.2** Secondary Objectives

- Assessment of CR rate, CRh rate, overall complete response rate (OCRR; CR, CRh, CRi [CRn, CRp], or MLFS), objective response rate (CR, CRh, CRi [CRn, CRp], MLFS, or PR), time to response and duration of response (DOR).
- To measure early mortality rates, overall survival (OS) and event-free survival (EFS).
- To determine the rate of eligible patients, per institution criteria, that transition to successful stem cell transplant after achieving overall complete response (CR, CRh, CRi [CRn, CRp], or MLFS).
- To assess rate of conversion to and maintenance of transfusion independence.
- To evaluate duration of initial hospitalization for flotetuzumab administration.
- To evaluate incidence and duration of hospitalizations subsequent to initial discharge.
- To monitor the safety and tolerability of flotetuzumab.
- To characterize the PK and immunogenicity of flotetuzumab.
- To determine safety and efficacy of tocilizumab in the treatment of IRR/CRS.

# **3.3 Exploratory Objectives**

- To evaluate CD123 expression on blast cells
- To evaluate circulating cytokine levels at baseline and over time
- To evaluate circulating leukemic and normal cells at baseline and over time
- To evaluate circulating T lymphocyte populations and activation markers at baseline and over time
- To evaluate leukemic cells, leukemic stem cells, normal progenitor cells and T lymphocytes at baseline and over time in the bone marrow
- To evaluate molecular markers of minimal residual disease (MRD)
- To examine changes in T lymphocyte repertoire
- To evaluate the correlation between cytogenetic abnormalities with responses to flotetuzumab immunotherapy.

- To study adaptive immune changes during flotetuzumab treatment.
- To study the tumor microenvironment (TME) immune contexture.

#### • Ruxolitinib Cohort Objectives:

- To characterize the onset, duration, and severity of IRR/CRS on an exploratory, pilot basis in flotetuzumab-treated patients receiving ruxolitinib and compare that to historical experience in patients not receiving ruxolitinib.
- To measure and compare cytokine profile and T-lymphocyte populations in patients receiving the combination of ruxolitinib and flotetuzumab vs flotetuzumab alone.
- To determine the safety and tolerability of the combination of ruxolitinib and flotetuzumab.

# 4 TRIAL DESIGN

# 4.1 Overall Study Design and Plan

This is an open-label, multi-dose, single-arm, multi-center, Phase 1/2, dose-escalation and expansion study to define an MTDS, describe preliminarily safety, and to assess PK, immunogenicity, immunomodulatory activity, and potential anti-neoplastic activity of flotetuzumab in patients with AML and MDS whose disease is not expected to benefit from cytotoxic chemotherapy.

This study is designed in three segments: The Single Patient Dose Escalation Segment (completed), followed by the Multi-patient Dose Escalation Segment (completed), and the MTDS Expansion Cohort Segment (ongoing). Two expansion cohorts were planned, one in AML and one in MDS. As of Amendment 7, the Sponsor stopped enrolling patients with MDS into this study. The primary objective of the study going forward is to assess anti-neoplastic activity of flotetuzumab in AML, as determined by the proportion of patients who achieve CR/CRh. Trial design aspects relating to continuation of the ongoing Cohort Expansion Segment, as of Amendment 11, are presented in this section. For a summary of prior study development see Section 2.3.2.

A total of approximately 283 patients will ultimately be enrolled in the Cohort Expansion segment, including:

- approximately 271 patients treated with flotetuzumab at 500 ng/kg/day;
- up to 12 patients in an exploratory mini-cohort treated with flotetuzumab at 500 ng/kg/day plus ruxolitinib.

As previously stated (Section 2.3.2.3), during Cohort Expansion, flotetuzumab is dosed as a continuous infusion following a multi-step lead-in dose in Cycle 1 Week 1. With Amendment 11 all cycles of flotetuzumab, whether induction or consolidation, will be administered as a continuous infusion in 28 day cycles (see Figure 5).

Starting with Cycle 2, patients who are benefiting from flotetuzumab treatment may continue to receive additional cycles of treatment with flotetuzumab, up to a maximum of 8 cycles in total. Benefit will be defined as a response of CR, CRh, CRi (CRn, CRp), morphologic leukemia-free state (MLFS), and PR. Patients with evidence of PD at the end of Cycle 1 may receive one further cycle to establish evidence of response (treat one cycle beyond PD), if tolerated and at the discretion of the investigator, prior to determining treatment failure. Continuation beyond Cycle 1 in these patients is justified given the mechanism of action of flotetuzumab. As is known with other immunotherapies, responses may be delayed compared to those seen with cytotoxic chemotherapy. In this study, 3/21 (14%) patients who achieved a CR did so after an initial increase (PD) in BM blast counts following Cycle 1.

Flotetuzumab dosing during the Cohort Expansion Segment consists of 2 treatment phases, "Induction" and "Consolidation" (see Figure 5).

**Induction** is comprised of Week 1 multi-step lead-in dosing of 30, 60, 100, 200, 300, 400, and 500 ng/kg/day flotetuzumab for 24 hours each for Days 1 through 7, followed by 500 ng/kg/day continuous IV infusion from Days 8 to 28 (Cycle 1). Patients who do not achieve a CR or CRh after the initial induction cycle (Cycle 1) may receive additional cycles (Cycles 2 - 6) of induction therapy. Further induction therapy consists of flotetuzumab at a dose of 500 ng/kg/day as a 7-day continuous IV infusion each week in each 28-day cycle, which does not include the lead-in dosing as in Cycle 1. Treatment may continue in 4-week cycles until:

- attainment of a CR or CRh,
- no evidence of anti-leukemic activity (PR or better, defined as 50% decrease in BM blasts or a decrease to between 5 and 25% blasts in the BM) after at least 2 successive cycles,
- evidence of progressive disease after one subsequent cycle of flotetuzumab following disease progression at the end of Cycle 1 (one cycle beyond progression),
- evidence of disease progression after achieving a response of PR,
- transition to stem cell transplant,
- the occurrence of DLT,
- death,
- exercise of Investigator discretion, or
- withdrawal of consent by the patient.

**Consolidation:** Patients who achieve a complete remission with complete or partial hematologic recovery (CR or CRh) after the induction cycle(s) may then receive up to 2 cycles of consolidation treatment consisting of flotetuzumab at 500 ng/kg/day dosed as a 7-day continuous IV infusion each week of a 28-day cycle.

Based on the judgment of the investigator, patients who achieve a CRi may receive one additional cycle of induction (not to exceed a total of 6 induction cycles), and then be considered for transition to consolidation.

At any point during induction or consolidation therapy a patient may transition to receive a stem cell transplant, if eligible per individual institution criteria. Patients who have completed treatment and are scheduled for a stem cell transplant may continue to receive flotetuzumab treatment until the time of the transplant.

Figure 5 Induction and Consolidation Treatment in the Expansion Cohort

Treatment after Cycle 1 Day 8 (and after a minimum of 24 hours at the 500 ng/kg/day maximum dose) may take place in the outpatient setting based on the patient's tolerance of therapy.

Safety evaluations will be conducted on an ongoing basis during the Cohort Expansion Segment of the study. Review by an Independent Data Monitoring Committee (IDMC, replacing the DSM previously involved in safety reviews), consisting of two physicians and one biostatistician, will be conducted in regular intervals. The interval analysis will utilize data from all cycles of treatment. If during the conduct of the interval cohort analysis, the Bayesian posterior probability is greater than 80% that the DLT (see Section 4.2) event rate is more than 20%, enrollment will be paused and an ad hoc meeting of the IDMC will be held to consider dose reduction or study termination. The IDMC will also review aggregate efficacy data for two planned interim analyses to determine enrollment continuation according to futility and efficacy boundaries described in Section 9.1.

## 4.1.1 Cohort Expansion Dosing

The highest incidence and severity of IRR/CRS is usually noted in the first week of dosing, with peak incidence around 48 to 72 hours post start of dosing; IRR/CRS was not typically observed beyond the first week of administration. In view of this, patients who experienced Grade 1 or 2 IRR/CRS that required minimal intervention, i.e., only anti-pyretics or antihistamines and after consultation between the treating Investigator and the Sponsor, may receive flotetuzumab as outpatients after Cycle 1 Day 8 (and after a minimum of 24 hours at the 500 ng/kg/day maximum dose). Following a dosing interruption for > 24 hours for any reason, patients are required to be hospitalized for the first 24-48 hours of dose re-initiation for observation and management of IRR/CRS. Once no IRR/CRS  $\geq$  Grade 2 is observed in a given patient, and they have otherwise demonstrated acceptable tolerability of the flotetuzumab regimen in the judgment of the Investigator, they may be considered for outpatient treatment without hospitalization for observation.

Flotetuzumab will be dosed using a multi-step lead-in dose approach for intrapatient dose escalation using multiple-step increments in dosing as follows: 30, 60, 100, 200, 300, 400 ng/kg/day each for 24 hours ( $\pm$  2 hours). On Day 7, the dose will be increased to 500 ng/kg/day and administered as a continuous infusion for the remainder of Cycle 1 (Table 2). Cycle 1 Week 2 and beyond will follow the Table 2 dosing schedule.

Patients that have a dosing interruption > 72 hours will reinitiate dosing with a modified multi-step lead-in dose starting at 30 ng/kg/day (followed by steps up to 60, 100, 200, 300, 400, and 500 ng/kg/day) with dose changes every 4-6 hours as tolerated.

Cycle	Week	Days	ng/kg/day
			Induction
		Day 1	30
		Day 2	60
1		Day 3	100
	Day 4	200	
1		Day 5	300
1		Day 6	400
		Day 7	500
	2	Days 8-14	500
	3 4	Days 15-21	500
		Days 22-28	500
		Additional Indu	iction Cycles, if appropriate
	1	Days 1 – 7	500
up to 5	2	Days 8 – 14	500
cycles	3	Days 15 – 21	500
	4	Days 22 – 28	500
		Additional Consol	lidation Cycles, if appropriate
	1	Days 1 – 7	500
up to 2	2	Days 8 – 14	500
cycles	3	Days 15 – 21	500
	4	Days 22 – 28	500

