#### General Administration Information:

**Flotetuzumab must not be administered as an IV push or bolus**. During the Cohort Expansion Phase, at least for the first 8 days of Cycle 1 (and after a minimum of 24 hours at the 500 ng/kg/day maximum dose), the drug will be administered in an inpatient hospital setting; but afterwards may be administered in an outpatient setting as described in **Section 4.1.1**. The type of pump used for administration of flotetuzumab may differ by country or region. It is important that at any point, THE INFUSION BAG CONTAINING FLOTETUZUMAB MUST NOT BE SHAKEN; excessive agitation may cause aggregate formation. Subsequent to Cycle 1 Day 8 (and after a minimum of 24 hours at the 500 ng/kg/day maximum dose), patients may, as appropriate (see **Section 6.3**), receive flotetuzumab as a continuous infusion in an outpatient setting using an ambulatory pump configuration. Specific instructions for dose preparation and administration in both the inpatient settings are provided in the Pharmacy Manual.

Sites must ensure patients who receive flotetuzumab in the outpatient setting will be provided instructions and trained appropriately and monitored for compliance and safety.

Flotetuzumab should not be admixed or diluted with other drugs. Any partially used vials or diluted dosing solutions should be discarded using appropriate drug disposal procedures.

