#### Dose interruption:

If dosing is interrupted for > 24 hours, the premedication schedule for Week 1 Day 1 should be followed (**Table 4**). If dosing is interrupted twice for > 24 hours, and the patient has no IRR/CRS upon each resumption of dosing, then no premedication is required after the third and subsequent interruptions. Patients that have a dosing interruption > 72 hours will reinitiate dosing with a modified multi-step lead-in dose starting at 30 ng/kg/day (followed by steps up to 60, 100, 200, 300, 400, and 500 ng/kg/day) with dose changes every 4-6 hours as tolerated.

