#### Table 5CRS Grading and Recommended Management Guidance

CRS Grade (26)	Dose Modification	Tocilizumab	Corticosteroids
Grade 1 Symptoms are not life threatening and require symptomatic treatment only, e.g., fever, nausea, fatigue, headache, myalgias, malaise	Slow infusion rate by 10-20%. After stabilization/resolution increase infusion rate as clinically indicated every 4-6 hours.	Administer tocilizumab (14) 8 mg/kg IV over 1 hour (not to exceed 800 mg/dose). If no clinical improvement in the signs and symptoms of CRS after the first dose, repeat tocilizumab every 8 hours as needed. Limit to a maximum of 3 doses in a 24-hour period; maximum total of 4 doses.	Administer dexamethasone (e.g., 4 to 6 mg IV or oral every 8 hours) for 24-48 hours.
Grade 2 Symptoms require and respond to moderate intervention Oxygen requirement < 40% or Hypotension responsive to fluids or low-dose of one vasopressor (Table 6) or Grade 2 organ toxicity	Slow infusion rate by 25-50%. After stabilization/resolution increase infusion rate as clinically indicated every 4-6 hours.	Per Grade 1	Manage per Grade 3 if no improvement or worsening within 24 hours after starting tocilizumab.
Grade 3 Symptoms require and respond to aggressive intervention Oxygen requirement ≥ 40% or Hypotension requiring high-dose vasopressors or multiple vasopressors (Table 6) or Grade 3 organ toxicity (except transaminitis) or Grade 4 transaminitis	Interrupt infusion, DO NOT FLUSH line. Aspirate residual drug from line. After resolution or stabilization to Grade 1 resume infusion at previous tolerated dose, and increase rate as clinically indicated every 4-6 hours.	Per Grade 1	Administer dexamethasone (e.g., 8 to 10 mg intravenously every 8 hours) or equivalent. Continue corticosteroid use until the event is Grade 1 or less, then taper over 3 days.

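### The required admission of 24 to 48 hours after a restart can end before the re-escalation does, and two rules give different restart doses after Grade 3 CRS when dosing resumes beyond 72 hours

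*Protocol*

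**What the plan says.** Four sets of instructions in the Protocol bear on restarting flotetuzumab in Cohort Expansion.

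- **Admission.** Section 4.1.1 covers every interruption longer than 24 hours, whatever its cause, and states: "patients are required to be hospitalized for the first 24-48 hours of dose re-initiation for observation and management of IRR/CRS". The next sentence allows outpatient treatment to be considered once the patient shows no IRR/CRS of Grade 2 or above and tolerates the regimen acceptably in the Investigator's judgment.
- **Re-escalation.** Section 6.4.1.1 (Dose interruption) states: "Patients that have a dosing interruption > 72 hours will reinitiate dosing with a modified multi-step lead-in dose starting at 30 ng/kg/day". Section 4.1.1 gives the same rule, lists the later levels up to 500 ng/kg/day and sets the pace: "with dose changes every 4-6 hours as tolerated". The Synopsis and Section 6.3 carry the same rule.
- **Outpatient condition.** Sections 4.1, 4.1.1, 6.2.1.2 and 8.2 and the Synopsis tie outpatient dosing to Cycle 1 Day 8 and to a further requirement: "and after a minimum of 24 hours at the 500 ng/kg/day maximum dose" (Section 6.2.1.2). None says whether this must be met again after a restart.
- **Grade 3 CRS.** The Grade 3 row of Table 5 interrupts the infusion, then: "After resolution or stabilization to Grade 1 resume infusion at previous tolerated dose". It sets no limit on the length of the interruption and does not refer to the 72-hour rule.

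**The concern.** The admission exists to observe and manage IRR/CRS, and Section 4.1.2 describes CRS as potentially life-threatening. The stay is the same for every restart after more than 24 hours, whether or not the patient has to climb again from 30 ng/kg/day. If the climb takes longer than the shortest permitted stay, a site can follow Section 4.1.1 to the letter and end the admission with dose increases still to come.

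The restart dose raises a second question. If dosing resumes more than 72 hours after an interruption for Grade 3 CRS, a site using Table 5 and a site using Sections 4.1.1 and 6.4.1.1 could restart the same patient at different doses.

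Patient safety is the main issue. Different readings across sites would also feed into reported summaries: dose intensity by cycle (Protocol 9.4, SAP 9), IRR/CRS incidence, severity and duration (Protocol 9.7.3, SAP 11.2.3), and hospitalization, a key secondary endpoint (Protocol 9.6.2.1, SAP 11.2.1).

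**Working it through.** The 24 to 48 hours is a rule and not a derived figure, so there is nothing to reproduce. The check compares it with elapsed times from the protocol's own steps.

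**Inputs (Section 4.1.1).** Dose levels 30, 60, 100, 200, 300, 400, 500 ng/kg/day: seven levels, six changes. Step interval *h* = 4 to 6 hours, or longer if not tolerated. Admission: 24 to 48 hours from restart. Outpatient condition: at least 24 hours at 500.

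**Formulas.** Time to reach 500 = 6 × *h*. Time to complete 24 hours at 500 = 6*h* + 24. Hours at 500 by hour 48 = 48 − 6*h*.

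| Step interval | 500 reached | Dose level just reached or current at 24 h | Hours at 500 by 48 h | 24 h at 500 complete |
|---|---|---|---|---|
| 4 h | 24 h | 500 (just reached) | 24 | 48 h |
| 5 h | 30 h | 300 | 18 | 54 h |
| 6 h | 36 h | 300 (just reached) | 12 | 60 h |

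A 24-hour stay ends no later than the moment 500 is reached. A 48-hour stay covers the whole climb at any of these intervals, but covers 24 further hours at 500 only with 4-hour steps. Slower steps lengthen every time in the table. For interruptions of 72 hours or less the modified lead-in does not apply, so this comparison does not arise.

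**Grade 3 CRS, by length of interruption.**

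1. Up to 72 hours: Table 5 gives the previous tolerated dose and the 72-hour rule is not triggered. No conflict.
2. Grade 3 CRS itself lasting 72 hours or more: outside the DLT exception in Section 4.2, so Section 6.3 withdraws the patient unless there are extenuating circumstances and continuing benefit. By default there is no restart.
3. Grade 3 CRS lasting under 72 hours and responding to treatment, so not a DLT, but dosing resumed after more than 72 hours, for example because recovery to Grade 1 took longer: both texts apply. Table 5 gives the previous tolerated dose; Sections 4.1.1 and 6.4.1.1 give 30 ng/kg/day. Section 6.3 repeats the 30 ng/kg/day restart for reinstitution after a second event of Grade 3 or above. No order of precedence is stated.

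**Size in case 3.** Ratio = previous tolerated dose ÷ 30. It is 30/30 = 1 at the bottom level, 400/30 = 13.3 if 400 was tolerated, and 500/30 = 16.7 at the top.

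**Effect on Cycle 1 dose.** Planned Cycle 1 total = (30 + 60 + 100 + 200 + 300 + 400 + 500) + 21 × 500 = 12,090 ng/kg. Take 400 as the previous tolerated dose and assume that both routes step up through the listed levels every *h* hours; Table 5 names the interval but not the levels. Over the 6*h* hours until both are at 500:

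- Table 5 route: (400 + 5 × 500) × *h*/24 = 2,900*h*/24
- 72-hour rule: (30 + 60 + 100 + 200 + 300 + 400) × *h*/24 = 1,090*h*/24
- Difference: 1,810*h*/24 = 302 ng/kg (*h* = 4) to 453 ng/kg (*h* = 6), or 2.5% to 3.7% of the planned cycle dose

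**The case against.** The strongest reply is that no patient faces incompatible instructions on admission. The 24 to 48 hours is a required stay with no stated maximum, so a site may keep the patient longer. The condition of 24 hours at 500 is written with Cycle 1 Day 8 and not for restarts. A patient who met it before the interruption can be read as bound only by the admission rule; one who had not can satisfy both rules by staying. Section 4.1.1 adds the tolerability condition, Section 6.4.1.1 calls for the Week 1 Day 1 premedication after an interruption of more than 24 hours (waived only from the third interruption, after two reaction-free resumptions), and the step interval is itself subject to tolerance.

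Most of this stands. A reader might infer that the admission rule contradicts the outpatient condition; the documents show only that their relation after a restart is unstated. The tolerability sentence mitigates partly: it does not say that the current re-escalation must be finished.

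A reader might also infer that patients would go home ahead of the peak that Section 4.1.1 describes, "with peak incidence around 48 to 72 hours post start of dosing". That sentence concerns the first week of dosing and adds that IRR/CRS was not typically seen later. The documents give no peak for re-exposed patients on the compressed lead-in, so the inference is an extrapolation.

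On Table 5, the overlap is narrow, the table belongs to guidelines that Section 6.4.1.2 lets the Investigator modify, and the 72-hour rule is consistent wherever it appears. What remains is a missing cross-reference, which matters because Table 5 is the natural place for a site to look after Grade 3 CRS.

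**Conclusion.** The point holds as two gaps in wording.

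First, after an interruption of more than 72 hours, 500 ng/kg/day is reached no earlier than 24 to 36 hours after restart. An admission ended at 24 hours is compliant although the patient is only just reaching 500 (4-hour steps) or 300 (6-hour steps). Whether the condition of 24 hours at 500 applies again is unstated; if it does, it is met only at 48 to 60 hours. This assumes that every step is taken on schedule.

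Second, for Grade 3 CRS lasting under 72 hours with dosing resumed after more than 72 hours, two texts give different restart doses and neither takes precedence. The ratio runs from 1 to about 16.7 with the previous tolerated dose. A 13-fold gap is one illustrative case and should not be read as typical.

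The documents do not give the number of patients affected. In the 400 ng/kg/day example the effect on Cycle 1 dose is a few percent per patient, and no effect on the primary CR/CRh test is shown. The reason to act is safety and uniform conduct across sites. I would rate this below a mandatory correction, with moderate confidence.

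**What to change.** Reconcile two sets of text.

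1. Sections 4.1, 4.1.1, 6.2.1.2 and 8.2, with the matching Synopsis text: state how the admission period relates to the modified lead-in, and whether the condition of 24 hours at 500 ng/kg/day applies again after a restart.
2. The Grade 3 row of Table 5 and the 72-hour rule in the Synopsis and Sections 4.1.1, 6.3 and 6.4.1.1: state which governs when both apply, and cross-refer.

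Which rule stands is for the sponsor's clinical team; no length of stay or dose is proposed here. The cost is wording in an amendment or site memo. Any change in inpatient days would depend on what the sponsor decides.
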